	Subacute hepatic failure	10056956
	Sugiura procedure	10083010
	Varices oesophageal	10056091
	Varicose veins of abdominal wall	10072284
	White nipple sign	10078438
Hepatitis, non-infectious	Acute graft versus host disease in liver	10066263
	Allergic hepatitis	10071198
	Alloimmune hepatitis	10080576
	Autoimmune hepatitis	10003827
	Chronic graft versus host disease in liver	10072160
	Chronic hepatitis	10008909
	Graft versus host disease in liver	10064676
	Hepatitis	10019717
	Hepatitis acute	10019727
	Hepatitis cholestatic	10019754
	Hepatitis chronic active	10019755
	Hepatitis chronic persistent	10019759
	Hepatitis fulminant	10019772
	Hepatitis toxic	10019795
	Immune-mediated hepatitis	10078962
	Ischaemic hepatitis	10023025

CCI

	Lupus hepatitis	10067737
	Non-alcoholic steatohepatitis	10053219
	Radiation hepatitis	10051015
	Steatohepatitis	10076331
Liver related investigations, signs and symptoms	Alanine aminotransferase abnormal	10001547
	Alanine aminotransferase increased	10001551
	Ammonia abnormal	10001942
	Ammonia increased	10001946
	Ascites	10003445
	Aspartate aminotransferase abnormal	10003477
	Aspartate aminotransferase increased	10003481
	AST/ALT ratio abnormal	10082832
	Bacterascites	10068547
	Bile output abnormal	10051344
	Bile output decreased	10051343
	Biliary ascites	10074150
	Bilirubin conjugated abnormal	10067718
	Bilirubin conjugated increased	10004685
	Bilirubin urine present	10077356
	Biopsy liver abnormal	10004792
	Blood bilirubin abnormal	10058477
	Blood bilirubin increased	10005364
	Blood bilirubin unconjugated increased	10005370
	Bromosulphthalein test abnormal	10006408
	Child-Pugh-Turcotte score abnormal	10077020
	Child-Pugh-Turcotte score increased	10068287
	Computerised tomogram liver abnormal	10078360
	Congestive hepatopathy	10084058
	Foetor hepaticus	10052554
	Galactose elimination capacity test abnormal	10059710
	Galactose elimination capacity test decreased	10059712
	Gamma-glutamyltransferase abnormal	10017688
	Gamma-glutamyltransferase increased	10017693
	Guanase increased	10051333
	Hepaplastin abnormal	10019621
	Hepaplastin decreased	10019622
	Hepatic artery flow decreased	10068997
	Hepatic enzyme abnormal	10062685
	Hepatic enzyme decreased	10060794
	Hepatic enzyme increased	10060795
	Hepatic function abnormal	10019670
	Hepatic hydrothorax	10067365
	Hepatic hypertrophy	10076254
	Hepatic mass	10057110
	Hepatic pain	10019705
	Hepatic sequestration	10066244
	Hepatic vascular resistance increased	10068358

CCI

	Hepatic venous pressure gradient abnormal	10083172
	Hepatic venous pressure gradient increased	10083171
	Hepatobiliary scan abnormal	10066195
	Hepatomegaly	10019842
	Hepatosplenomegaly	10019847
	Hyperammonaemia	10020575
	Hyperbilirubinaemia	10020578
	Hypercholia	10051924
	Hypertransaminasaemia	10068237
	Kayser-Fleischer ring	10023321
	Liver function test abnormal	10024690
	Liver function test decreased	10077677
	Liver function test increased	10077692
	Liver induration	10052550
	Liver palpable	10075895
	Liver scan abnormal	10061947
	Liver tenderness	10024712
	Magnetic resonance imaging liver abnormal	10083123
	Magnetic resonance proton density fat fraction measurement	10082443
	Mitochondrial aspartate aminotransferase increased	10064712
	Molar ratio of total branched-chain amino acid to tyrosine	10066869
	Oedema due to hepatic disease	10049631
	Perihepatic discomfort	10054125
	Retrograde portal vein flow	10067338
	Total bile acids increased	10064558
	Transaminases abnormal	10062688
	Transaminases increased	10054889
	Ultrasound liver abnormal	10045428
	Urine bilirubin increased	10050792
	White nipple sign	10078438
	X-ray hepatobiliary abnormal	10056536
Hypertension	Accelerated hypertension	10000358
	Blood pressure ambulatory increased	10005732
	Blood pressure diastolic increased	10005739
	Blood pressure inadequately controlled	10051128
	Blood pressure increased	10005750
	Blood pressure management	10063926
	Blood pressure orthostatic increased	10053355
	Blood pressure systolic increased	10005760
	Catecholamine crisis	10081751
	Dialysis induced hypertension	10063067
	Diastolic hypertension	10012758
	Eclampsia	10014129
	Endocrine hypertension	10057615
	Essential hypertension	10015488
	Gestational hypertension	10070538
	HELLP syndrome	10049058

	Hyperaldosteronism	10020571
	Hypertension	10020772
	Hypertension neonatal	10049781
	Hypertensive angiopathy	10059238
	Hypertensive cardiomegaly	10020801
	Hypertensive cardiomyopathy	10058222
	Hypertensive cerebrovascular disease	10077000
	Hypertensive crisis	10020802
	Hypertensive emergency	10058179
	Hypertensive encephalopathy	10020803
	Hypertensive end-organ damage	10079496
	Hypertensive heart disease	10020823
	Hypertensive nephropathy	10055171
	Hypertensive urgency	10058181
	Labile hypertension	10049079
	Malignant hypertension	10025600
	Malignant hypertensive heart disease	10025603
	Malignant renal hypertension	10026674
	Maternal hypertension affecting foetus	10026924
	Mean arterial pressure increased	10026985
	Metabolic syndrome	10052066
	Neurogenic hypertension	10067598
	Orthostatic hypertension	10065508
	Page kidney	10076704
	Postoperative hypertension	10050631
	Pre-eclampsia	10036485
	Prehypertension	10065918
	Procedural hypertension	10062886
	Renal hypertension	10038464
	Renal sympathetic nerve ablation	10074864
	Renovascular hypertension	10038562
	Retinopathy hypertensive	10038926
	Secondary aldosteronism	10039808
	Secondary hypertension	10039834
	Supine hypertension	10078932
	Systolic hypertension	10042957
	Withdrawal hypertension	10048007
Proteinuria	Albumin globulin ratio increased	10001567
	Albumin urine present	10001582
	Albuminuria	10001580
	Bence Jones protein urine present	10053112
	Bence Jones proteinuria	10004231
	Beta 2 microglobulin urine increased	10004501
	Globulinuria	10018352
	Microalbuminuria	10027525
	Myoglobinuria	10028629
	Orthostatic proteinuria	10031129

CCI

	Protein urine	10037018
	Protein urine present	10053123
	Proteinuria	10037032
	Urine albumin/creatinine ratio increased	10053541
	Urine protein/creatinine ratio abnormal	10053539
	Urine protein/creatinine ratio increased	10053538
Thyroid dysfunction	Basedow's disease	10004161
	Endocrine ophthalmopathy	10060742
	Exophthalmos	10015683
	Hashitoxicosis	10067873
	Hyperthyroidism	10020850
	Immune-mediated hyperthyroidism	10083517
	Inappropriate thyroid stimulating hormone secretion	10075007
	Malignant exophthalmos	10075386
	Marie Lenhart syndrome	10068828
	Primary hyperthyroidism	10075899
	Secondary hyperthyroidism	10053260
	Thyroid dermatopathy	10069771
	Thyroid tuberculosis	10043774
	Thyrotoxic cardiomyopathy	10075043
	Thyrotoxic crisis	10043786
	Thyrotoxic myopathy	10081524
	Thyrotoxic periodic paralysis	10043788
	Toxic goitre	10075050
	Toxic nodular goitre	10044242
	Anti-thyroid antibody	10060325
	Anti-thyroid antibody positive	10060310
	Antithyroid arthritis syndrome	10073029
	Autoimmune thyroid disorder	10079165
	Autoimmune thyroiditis	10049046
	Biopsy thyroid gland abnormal	10004889
	Blood thyroid stimulating hormone abnormal	10005830
	Blood thyroid stimulating hormone decreased	10005832
	Blood thyroid stimulating hormone increased	10005833
	Butanol-extractable iodine decreased	10006818
	Butanol-extractable iodine increased	10006819
	Congenital thyroid disorder	10076602
	Euthyroid sick syndrome	10015549
	Free thyroxine index abnormal	10050747
	Free thyroxine index decreased	10050748
	Free thyroxine index increased	10050749
	Gamma radiation therapy to thyroid	10017685
	Goitre	10018498
	Hashimoto's encephalopathy	10069432
	Immune-mediated thyroiditis	10083071
	Infectious thyroiditis	10071250
	Iodine uptake abnormal	10022918

Iodine uptake decreased	10022920
Iodine uptake increased	10022922
Orbital decompression	10072141
Photon radiation therapy to thyroid	10034957
Polyglandular autoimmune syndrome type II	10036073
Polyglandular autoimmune syndrome type III	10064115
Protein bound iodine decreased	10037001
Protein bound iodine increased	10037002
Radioactive iodine therapy	10037784
Radiotherapy to thyroid	10062098
Reverse tri-iodothyronine decreased	10060307
Reverse tri-iodothyronine increased	10060306
Silent thyroiditis	10079012
Thyreostatic therapy	10065359
Thyroglobulin absent	10054025
Thyroglobulin decreased	10054011
Thyroglobulin increased	10054010
Thyroglobulin present	10054024
Thyroid disorder	10043709
Thyroid dysfunction in pregnancy	10056525
Thyroid electron radiation therapy	10043722
Thyroid function test abnormal	10043730
Thyroid gland scan abnormal	10062149
Thyroid hemiagenesis	10077609
Thyroid hormone replacement therapy	10068076
Thyroid hormones increased	10063161
Thyroid operation	10062126
Thyroid pain	10043757
Thyroid releasing hormone challenge test abnormal	10043764
Thyroid stimulating immunoglobulin increased	10071389
Thyroid therapy	10065358
Thyroidectomy	10062127
Thyroiditis	10043778
Thyroiditis acute	10043780
Thyroiditis chronic	10043781
Thyroiditis fibrous chronic	10043782
Thyroiditis subacute	10043784
Thyroxin binding globulin abnormal	10051423
Thyroxin binding globulin decreased	10051421
Thyroxin binding globulin increased	10051420
Thyroxine abnormal	10043814
Thyroxine decreased	10043816
Thyroxine free abnormal	10055158
Thyroxine free decreased	10055162
Thyroxine free increased	10055163
Thyroxine increased	10043818
Thyroxine therapy	10052702

Tri-iodothyronine abnormal	10044592
Tri-iodothyronine decreased	10044594
Tri-iodothyronine free abnormal	10053794
Tri-iodothyronine free decreased	10053791
Tri-iodothyronine free increased	10053790
Tri-iodothyronine free normal	10053793
Tri-iodothyronine increased	10044596
Tri-iodothyronine uptake abnormal	10062215
Tri-iodothyronine uptake decreased	10044601
Tri-iodothyronine uptake increased	10044602
Ultrasound thyroid abnormal	10060987
X-ray therapy to thyroid	10048207
Autoimmune hypothyroidism	10076644
Congenital hypothyroidism	10010510
Generalised resistance to thyroid hormone	10018096
Hypothyroidic goitre	10059844
Hypothyroidism	10021114

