Grade 2: 2+ or 3+ proteinuria; urinary protein 1.0 - 2.0 g (excluding 2.0 g)/24 hours	None.	Provide supportive treatment and increase the frequency of urine monitor to once a week; consult nephrologist if necessary.
Grade 2: Proteinuria \geq 2+; urinary protein 2.0 - 3.5 g (excluding 3.5 g)/24 hours	Hold surufatinib treatment and resume treatment at the same dose level if proteinuria resolves to \leq Grade 1 within 21 days	Provide supportive treatment and increase the frequency of urine monitor to once a week; consult nephrologist if necessary.
Grade 3: Urinary protein \geq 3.5 g/24 hours	Hold surufatinib. If test results resolves to \leq Grade 1 within 21 days, resume at a lower dose.	Provide supportive treatment and increase the frequency of urine monitor to once or twice a week; consult nephrologist if necessary.

^a If urine dipstick reveals proteinuria 2+, 24-hour urine collection should be performed for determination of total protein within one week. The CTCAE grade recorded for proteinuria should be determined by the 24-hour urine collection, however the start date of the AE will be recorded as the first instant of proteinuria (i.e. urine dipstick). If surufatinib dose has been reduced to 200mg QD and a further dose reduction is required for recurrent proteinuria, keep the same daily dose of 200 mg QD of surufatinib for 3 consecutive weeks followed by 1-week drug holiday and repeat for each treatment cycle, (i.e. 3 weeks on and 1 week off; every 4 weeks constitutes a treatment cycle). If proteinuria cannot resolve to \leq Grade 1 after a dose interruption of 21 days, continuation/resumption of surufatinib treatment should be discussed with the medical monitor. Surufatinib treatment should be discontinued if a patient develops nephrotic syndrome.

Table 9 Dose Modification for Liver Function Impairment

Grade and Definitions	Dose Adjustment	Suggested Actions
Grade 1: ALT >1-3 \times ULN or AST >1-3 \times ULN	None.	Follow up per planned schedule. Check total bilirubin. ^a
Grade 2: ALT >3-5 \times ULN or AST >3-5 \times ULN	Maintain the original dose, provide supportive care of complications of liver impairment, observation for 1 week, If the ALT and AST is	Check total bilirubin. ^a Provide supportive care and increase the frequency of liver function monitor to 1-2 times a week.

Table 9 Dose Modification for Liver Function Impairment

Grade and Definitions	Dose Adjustment	Suggested Actions

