9.8 Diagnosis vs Symptom and Signs

If known, a diagnosis should be recorded on the CRF rather than individual signs and symptoms (eg, record only liver failure or hepatitis rather than jaundice, asterixis, and elevated transaminases). However, if a constellation of signs and/or symptoms cannot be medically characterized as a single diagnosis or syndrome at the time of reporting, each individual event should be recorded as an AE or SAE on the CRF. If a diagnosis is subsequently established, it should be reported as follow-up information.

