17.1.5. TEAEs Of Special Interest (TEAESI)

The preferred terms for TEAESI are included in Appendix 2. Summaries of incidence (frequencies and percentages) of TEAESIs by Standardized MedDRA Queries (SMQ) and PT based on the [Appendix 2](#) will be prepared. The broad search will be used for SMQ terms. Time to TEAESI onset is defined as time interval from date of first administration of study medication to the earliest onset date among TEAEs within the same SMQ. Time to TEAESI onset will be summarized by SMQ for each dose cohort and disease cohort.

AESIs will be flagged and included in a listing of AEs.

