APPENDIX 2. ADVERSE EVENTS OF SPECIAL INTEREST

AESI SMQ	PT Term	PT Code
Acute renal failure	Acute kidney injury	10069339
	Acute phosphate nephropathy	10069688
	Anuria	10002847
	Azotaemia	10003885
	Continuous haemodiafiltration	10066338
	Dialysis	10061105
	Foetal renal impairment	10078987
	Haemodialysis	10018875
	Haemofiltration	10053090

CCI

	Neonatal anuria	10049778
	Nephropathy toxic	10029155
	Oliguria	10030302
	Peritoneal dialysis	10034660
	Prerenal failure	10072370
	Renal failure	10038435
	Renal failure neonatal	10038447
	Renal impairment	10062237
	Renal impairment neonatal	10049776
	Subacute kidney injury	10081980
Haemorrhages	Abdominal wall haematoma	10067383
	Abdominal wall haemorrhage	10067788
	Abnormal withdrawal bleeding	10069195
	Achenbach syndrome	10079562
	Acute haemorrhagic leukoencephalitis	10058994
	Acute haemorrhagic ulcerative colitis	10075634
	Administration site bruise	10075094
	Administration site haematoma	10075100
	Administration site haemorrhage	10075101
	Adrenal haematoma	10059194
	Adrenal haemorrhage	10001361
	Anal fissure haemorrhage	10079765
	Anal haemorrhage	10049555
	Anal ulcer haemorrhage	10063896
	Anastomotic haemorrhage	10056346
	Anastomotic ulcer haemorrhage	10002244
	Aneurysm ruptured	10048380
	Angina bullosa haemorrhagica	10064223
	Anorectal varices haemorrhage	10068925
	Anticoagulant-related nephropathy	10083346
	Aortic aneurysm rupture	10002886
	Aortic dissection rupture	10068119
	Aortic intramural haematoma	10067975
	Aortic perforation	10075729
	Aortic rupture	10060874
	Aponeurosis contusion	10075330
	Application site bruise	10050114
	Application site haematoma	10068317
	Application site haemorrhage	10072694
	Application site purpura	10050182
	Arterial haemorrhage	10060964
	Arterial intramural haematoma	10074971
	Arterial perforation	10075732
	Arterial rupture	10003173
	Arteriovenous fistula site haematoma	10055150
	Arteriovenous fistula site haemorrhage	10055123
	Arteriovenous graft site haematoma	10055152

CCI

Arteriovenous graft site haemorrhage	10055126
Astringent therapy	10067372
Atrial rupture	10048761
Auricular haematoma	10003797
Basal ganglia haematoma	10077031
Basal ganglia haemorrhage	10067057
Basilar artery perforation	10075736
Bladder tamponade	10062656
Bleeding varicose vein	10005144
Blood blister	10005372
Blood loss anaemia	10082297
Blood urine	10005863
Blood urine present	10018870
Bloody discharge	10057687
Bloody peritoneal effluent	10067442
Bone contusion	10066251
Bone marrow haemorrhage	10073581

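### An event recorded only as nephrotic syndrome would not count as a proteinuria event of special interest, because Appendix 2 as shown does not list the term

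*SAP*

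**What the plan says.** **How the events are selected.** SAP 17.1.5 states "The preferred terms for TEAESI are included in Appendix 2". It plans incidence by standardised MedDRA query (SMQ) and preferred term, and adds "The broad search will be used for SMQ terms". It also plans onset: "Time to TEAESI onset will be summarized by SMQ for each dose cohort and disease cohort". Onset is the earliest date among events within the same SMQ. No severity breakdown is stated for these events.

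**What the groups contain.** The Proteinuria group in Appendix 2 runs from "Albumin globulin ratio increased" to "Urine protein/creatinine ratio increased". It sits between the Hypertension and Thyroid dysfunction groups, so it can be read in full. The other renal group, Acute renal failure, includes terms such as "Nephropathy toxic".

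**What the protocol says of nephrotic syndrome.** The footnote to Table 8, the proteinuria dose-modification table in Protocol 7.2.3, reads "Surufatinib treatment should be discontinued if a patient develops nephrotic syndrome".

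**How events are recorded.** Protocol 9.8 says "If known, a diagnosis should be recorded on the CRF rather than individual signs and symptoms", with a diagnosis made later reported as follow-up. Protocol 9.11 adds that where a clinically significant laboratory abnormality is a sign of a syndrome, only the diagnosis has to be entered.

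**The concern.** The protocol places nephrotic syndrome within its handling of proteinuria and attaches a discontinuation instruction to it, but the list that defines the proteinuria events of special interest does not contain it. The recording rules prefer a diagnosis to its component signs. A site that follows them can enter nephrotic syndrome alone, and that entry matches no listed term.

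Proteinuria is named as an identified risk in Protocol 3.3. Protocol 2.3 reports it as leading to discontinuation in 2.0% of the 714 monotherapy patients. At stake is whether the dedicated proteinuria incidence and onset summaries are complete, in arms small enough for a single patient to be visible.

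**Working it through.** The plan states no figure on this point. The check is a reading of the lists, followed by simple arithmetic on size.

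**1. Term lists (SAP Appendix 2).**

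| Group | Terms listed | Nephrotic syndrome listed? |
|---|---|---|
| Proteinuria | 16 | No |
| Acute renal failure | 19 | No |
| Other groups in the text available | – | No |

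The text available breaks off in the thyroid terms, so a later group cannot be excluded. The Proteinuria group itself is complete.

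**2. Comparison with another group.** Table 7 of the protocol gives malignant hypertension and hypertensive crisis as examples of Grade 4 hypertension, for which drug is discontinued. Both are preferred terms in the Hypertension group. The Proteinuria group has no corresponding entry for the diagnosis named under Table 8, and the SAP gives no reason for the difference.

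**3. What happens to a patient, by recording path.**

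| Path | Counted as a proteinuria event? | Onset date |
|---|---|---|
| Proteinuria entered and kept; nephrotic syndrome added | Yes | Unchanged (proteinuria start date) |
| Grade 3 proteinuria (3.5 g/24 h or more) entered as proteinuria | Yes | Unchanged |
| Proteinuria entry re-termed as nephrotic syndrome | No | Lost |
| Nephrotic syndrome is the only entry | No | Lost |

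The last path is permitted by Protocol 9.8 and 9.11. The third is neither required nor excluded: 9.8 does not say what becomes of the earlier entry.

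**4. Size of one lost patient.** The change in incidence is 1/n. Using the planned arm sizes in Protocol 10.1:

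- pNET or epNET, n = 15: 1/15 = 6.7 percentage points
- BTC, n = 30: 1/30 = 3.3 points
- STS, n = 55: 1/55 = 1.8 points

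These are the weights of one patient, not estimates of effect. The NET arm sizes are minimums, and SAP section 6 pools in escalation patients with the same tumour type treated at the recommended dose. Actual denominators may therefore be larger and the weights smaller.

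**5. How many patients.** The documents give no count. Protocol 2.3 does not name nephrotic syndrome among discontinuation reasons at 1% or more, or among the common serious events at 1% or more. If its rate is assumed to be below 1%, expected cases are below 0.01 × 15 = 0.15, 0.01 × 30 = 0.30 and 0.01 × 55 = 0.55 per arm. The discontinuation list may not be exhaustive, so this is an assumption. Only cases on the last two paths would be lost.

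**The case against.** The strongest reply is that the protocol already expects a separate proteinuria entry. The Table 8 footnote takes the grade from the 24-hour collection and dates the event from the first positive dipstick. Protocol 8.1.3 requires that collection within a week of a 2+ result. Protocol 9.10 adds a new entry when a persistent event worsens. Most patients who reach nephrotic syndrome should therefore already have a proteinuria entry, and for them neither incidence nor onset changes. This stands, and it is why the point is conditional.

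A second reply is that nothing disappears from the safety report. The event would still appear by preferred term in the summary of all events (SAP 17.1.1), in the discontinuation summary (17.1.2) if drug is withdrawn for it, and in the serious-event summary (17.1.4) if serious. This also stands.

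A third is that the protocol fixes no term list, and the SAP uses the broad search. The first half is true. On the second, 17.1.5 ties the terms to Appendix 2, and nothing says the search adds to them. If it did, Appendix 2 would be incomplete and would still need the line. Whether the standard query contains the term cannot be settled from these documents.

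A reader might go further and infer that the most severe proteinuria falls out of the group and that its incidence is biased towards mild cases. The documents do not support this. Grade 3 proteinuria entered under that name stays in, no rule requires the earlier entry to be overwritten, and the planned summaries of these events carry no severity breakdown that could be distorted.

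**Conclusion.** The gap is real but narrow. An event whose only record is nephrotic syndrome would not be a proteinuria event of special interest under SAP 17.1.5, although the protocol deals with that diagnosis in its proteinuria table. The loss is limited to the special-interest incidence and time-to-onset tables, by one patient's weight per case, and the number of cases may be zero.

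The conclusion rests on three assumptions: that Appendix 2 is the operative list, that no group beyond the text available holds the term, and that at least one site records the diagnosis alone or re-terms an earlier entry. Severity is minor; the change is worth making because it is cheap and removes a dependence on how sites record.

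**What to change.** Add the preferred term Nephrotic syndrome to the Proteinuria group in SAP Appendix 2, marked as a sponsor-defined supplement to the SMQ. Footnote the incidence and time-to-onset tables to say so, and report the count without the supplement as well, so that the figure stays comparable with the SMQ alone.

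The cost is one line in the appendix, the matching entry in the programming lookup, and a footnote. The SAP history shows that Appendix 2 was already updated in versions 2.0 and 2.2, so this is routine if done before database lock. The downside is a small departure from the SMQ and a proteinuria figure that may be slightly less favourable. No dosing or stopping rule is affected.
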